Acceptance and Commitment Therapy with Enhanced Mindfulness for Chronic Pain

Trondheim, Norway June 15, 2018

1. Project title

Acceptance and commitment therapy with and without enhanced mindfulness training for chronic pain: A randomized controlled efficacy and mediator study

2. Introduction

During the last three decades numerous population-based surveys have presented surprisingly high prevalence figures of chronic pain, according to a recent systematic review (1). Our united Norwegian pain research group has estimated figures in Norway between 24 (2) and 29% (3) of chronic pain and a pooled prevalence of 31% worldwide (1). Chronic pain is estimated to affect 100 million adult Americans at any given time and carries direct and indirect costs of over 600 billion dollars annually in U.S. alone (4). In Sweden the costs are estimated to be 32 billion EUR per year (5). Despite this, and the fact that The Global Burden of Disease studies show that chronic pain conditions are the most important current and future causes of morbidity and disability across the world (6), little has so far been done. Treatment measures that have been initiated, like opioid treatment and repeated blocks, have not alleviated this significant health and societal problem. On the contrary, widespread use of opioids against chronic non-malignant pain has caused a fatal opioid epidemic in the US (7). Pharmacological pain management is still indicated for chronic nociceptive and neuropathic pain, but in most cases of chronic pain, no cause can be identified. In a major clinical examination study of chronic pain in the general population, our research group has confirmed that in more than fifty percent of the cases, musculoskeletal pain conditions dominate and no cause for the pain condition can be identified (8).

As non-pharmacological alternatives, psychosocial treatments have been recommended for chronic pain management (9). One such treatment is Acceptance and Commitment Therapy (ACT). ACT is based on Relational Frame Theory (RFT), a comprehensive theory about language and cognition (10). Treatment intends to help patients identify values ("what is truly meaningful to them") and to set goals and take action according to their values. In addition, patients are taught mindfulness skills to increase acceptance of pain, thoughts and feelings so that they have less impact on functioning and action, but addition of daily mindfulness training at home is not included (10). ACT is considered a "third generation" variant of cognitive behavior therapy and has research support in the treatment of several mental health problems (11). Among patients with chronic pain, several small clinical trials have shown that ACT is superior to controls in terms of increasing function and improving mental health, with small to medium effect sizes (12). However, further methodologically robust trials are required (13). The primary aim of this study is thus to examine in a large sample of patients from four multidisciplinary pain centers whether ACT for chronic pain is more effective than a patient education program, and whether adding daily mindfulness training will improve the outcome.

The question is, however, not only if it is effective, but "why, for whom, and under what circumstances?". Mediators and moderators of change are important to sort out. Identifying specific variables that mediate the effects of a treatment on patient outcome could facilitate refinement of theoretical models and the development of more effective treatments. Minimal research has so far been conducted with the aim to identify treatment effect moderators such as patient characteristics (phenotypes) that help us to match patients to appropriate and effective treatments. This is supposed to be one of the most important directions for future research in chronic pain (14-16). Secondary aims are thus to identify for whom the treatment works, for whom it is not effective, and to identify key mechanisms of change so that more effective variants of the treatment can be developed.

Current theories of chronic pain emphasize an important role for attentional processes (17). Attention is often subdivided into three independent networks : 1) alerting- which is readiness in preparation for an impending stimulus, including tonic effects that result from spending time on a task (vigilance) and phasic effects that are due to brain changes induced by warning signals or targets, 2) orienting- which is the selection of specific information from multiple sensory stimuli, and 3) executive attention- which is monitoring and resolution of conflict between activity in different neural areas (18). Alerting involves the brain's noradrenaline system, which originates in the brain stem and mainly in the locus coeruleus. Orienting involves frontal and parietal areas, including the frontal visual fields and inferior and superior parietal lobe. Executive attention involves the anterior cingulate cortex, anterior insula and basal ganglia (19, 20). Several recent studies have shown that patients with chronic pain have an attentional bias towards painful stimuli and other negative information (21-23). Moreover, recent meta-analyses have shown that patients with chronic pain have reduced executive function including working memory deficits (24, 25). Recently it has also been demonstrated that attentional functioning predicts chronic pain (26).

Mindfulness is typically described as non-judgmental attention to experiences in the present moment (27). It includes two modes of action: First, it requires the regulation of attention in order to maintain focus on immediate experiences such as thoughts, emotions, body posture and sensations. Second, it requires the ability to approach one's own experience with openness and acceptance. Practicing mindfulness meditation may enhance attentional control, alter self-awareness and improve emotion regulation. A systematic review found that early phases of mindfulness training might be associated with improvements in executive attention and orienting, while later phases might be more associated with improved alerting (28).

Three studies have used neuroimaging to evaluate changes in pain processing through mindfulness training. Beginners showed increased activity in anterior cingulate cortex and anterior insula which are areas involved in the cognitive regulation of nociceptive processing, increased activity in the orbitofrontal cortex which is involved in reframing the evaluation of stimuli and reduced activity in the primary somatosensory cortex (29). Experienced users of mindfulness training showed decreased activity in dorsolateral and ventrolateral prefrontal cortex and increased activity in primary pain processing areas such as the insula, somatosensory cortex and thalamus (30, 31). These findings suggest that mindfulness training alters the brain differently over time and has significant influence on cognitive processing over time. Although it is documented that brain regions relevant for the regulation of attention and pain show functional and structural changes following mindfulness training, it is not known whether these changes are actually related to improvements in attentional functioning and clinical outcomes among patients with chronic pain. If it turns out to be so, one may have discovered a major mechanism of change in pain processing and symptom reduction. Thus, one main aim of the present study is to examine if mindfulness training improves attentional functioning and if this potential improvement enhances the amelioration of pain.

In ACT, mindfulness is included in ways to increase acceptance and psychological flexibility, but does not necessarily involve systematic practice over time(10). We will therefore investigate the effects of adding prolonged mindfulness training to ACT delivered to patients with chronic pain. Since mindfulness training may affect the brain differently over time, it is important to measure attentional functioning after early phases of mindfulness training (after four weeks) and after training systematically over a longer period (six and twelve months).

Although improvement of attentional functioning may be a central mechanism of change (group level), it may not be an important mechanism of change in all patients (individual level). Several mechanisms, biological, psychological and social, have been suggested to maintain chronic pain

(32). It is reasonable to assume that all these mechanisms are more or less important in different pain conditions, in patients with different psychological makeups and patients living under different social and occupational circumstances. Some have argued for applying personalized or individualized treatment (33). As stated by Jensen in a comprehensive review in Pain (9): “If a clinician limits himself or herself to only one of the existing theoretical models or psychosocial treatments, then a subset of that clinician’s patients will be unlikely to receive optimum care.” We assume that it is vital to examine and diagnose each patient thoroughly in a standardized way before the start of a treatment trial to make it possible to identify common characteristics of patients who do not benefit much from the treatments (predictors of poor outcome). It also makes it possible to identify characteristics of patients who may profit more from one treatment than the other treatments (differential treatment effects). This is a second aim of the present study, namely to identify clinical predictors and moderators of change and possibly to identify distinct phenotypes.

The research project has several methodological strengths:

1. This will be the largest controlled study on ACT for chronic pain so far. Most patients with chronic pain without known cause referred to all the four major multidisciplinary pain centers in all health regions of Norway will be asked to participate in the study.
2. The patients will receive high quality evidence based assessments by clinical experts specifically trained in pain diagnosis and given treatment conducted by highly qualified therapists with adequate training. Improvement in the quality of clinical practice in all regions in a standardized way will be the result immediately from the start of the project.
3. This multisenter study will have coordinated data and equal treatment implementation since the four multidisciplinary pain centers already coincide with diagnosis, assessment and treatment. In the fall of 2017 they had a two-day meeting where all four presented their ACT group program for closer co-operation. Thus, the multicenter study is therefore highly feasible.
4. The four centers have a response rate on internet-based self-report on almost 100% pre-admission and about 80% one year after treatment from four identical online quality records. This self-report system will be used in the study and has been published as feasible by our research group (34).
5. It should be possible to identify patient characteristics (phenotypes) that can guide clinicians in the future in the selection of which of the patients are likely to profit from ACT, and which patients are likely to receive benefits from the addition of mindfulness training.
6. It should also be possible to identify patients who benefit less from the treatments and who may need other alternatives. Patient characteristics can help us to identify key target components in the development of new treatments for these patients.
7. The theoretical hypothesis aiming to identify a key mediator of change is based on modern cognitive neuroscience including thorough neurobiological studies of the human brain.
8. Both for self-report measures and attentional functioning the study will use safe computerized test systems the patients can complete in their homes. This will make it possible to increase the number of assessments without the subjects needing to return to the outpatient clinic. This will increase the quality of assessments and reduce the cost
9. Since the study includes self-report assessment methods that are easy to deliver and score, it is also easy to translate the knowledge and procedures to other treatment facilities in Norway and internationally after the project period.

2.1 Need description

Patients referred to tertiary multidisciplinary pain clinics are those who generally have very poor functioning and they have often tried many standard treatments without effect. Many have experienced unsatisfactory or adverse effects of medication. To establish the efficacy of a psychological therapy would be of major benefit for this group of patients living with refractory

chronic pain. This multi-professional study has the potential to strengthen the disciplines by increasing our knowledge about efficacy of an increasingly popular psychological treatment. If shown efficacious and feasible, this study should provide evidence for educating other therapists working with chronic pain patients in the method. Investigating key methods of change may give knowledge necessary for developing and improving the therapeutic method.

3. Hypotheses, aims and objectives

The primary aim of the study is to investigate the effectiveness of ACT (group 1) and whether adding a component of mindfulness training (group 2) will improve outcomes on pain (primary outcome), attentional functioning, physical functioning and mental health (secondary outcomes), compared to a control group (group 3). A secondary aim is to assess the degree to which improvement in attentional functioning can act as a mechanism of change (mediator) in pain. A third aim is to identify patient characteristics (phenotypes) that predict treatment effects (moderators of change), or, equally important, that predict failure to achieve benefit.

More specifically it is hypothesized that:

1. ACT is more effective in improving pain (primary outcome), mental health and physical function (secondary outcomes) at 52 weeks compared to the controls (paper 1).
2. ACT with an additional component of mindfulness training will be significantly more effective in reducing pain and improving mental health and physical functioning at 52 weeks than ACT without mindfulness training (paper 1).
3. Patients receiving ACT with mindfulness training will from treatment start to treatment termination show significant improvement in orienting and executive attention reflecting enhancement in top down processing compared to those receiving ACT without mindfulness training and compared to control (paper 2).
4. Patients receiving mindfulness training and continuing to practice until 32 weeks of follow-up will show significant improvement in alerting, reflecting enhancement in bottom up processing at 52 weeks follow-up compared to those who have discontinued practicing (paper 2).
5. Patient improvement in alerting and executive attention during treatment predicts a reduction in pain at eight and 16 weeks of follow up (paper 3).
6. Patients who continue to practice mindfulness training until 32 weeks of follow-up will report less pain at 52 weeks follow up compared to those who do not (paper 3).
7. Patients with initial higher levels of attentional functioning, will report a significantly higher reduction in pain and improvement in physical functioning and mental health (paper 4).
8. Patients with neuropathic pain, psychiatric and sleep disorders will have a worse outcome independent of treatment received (17) (paper 4).
9. The cost effectiveness of ACT for chronic pain is superior to patient education (paper 5).
10. Effects of ACT are maintained at three years follow up (paper 6).

4. Project methodology

4.1 Project arrangements, method selection and analyses

4.1. 1. Sample

At least 486 patients will be included in the study (see power analyses below). Patients will be included if they are referred to one of the pain clinics with a primary diagnosis of chronic pain lasting for at least six months. About 200 patients will be recruited from Oslo, 200 from Trondheim, 100 from Bergen, and 100 from Tromsø. Exclusion criteria will be severe somatic disease or severe mental disorder (ongoing mania, psychosis, suicidal ideation or substance abuse/addiction). In addition will patients who cannot communicate in Norwegian or who need 24-hour personal assistance be excluded. Each treatment center will randomize the patients into three different research programs (see below).

4.1.2. Study design

This is a three group randomized controlled trial with 162 patient in each group, six different measurement points, of which pre-treatment and 52 weeks after start of the treatment are the crucial points.

4.1.3 Background for the interventions

The choice of treatment conditions is based on the following reasons: 1. Mindfulness training has shown to be effective in both stress and pain reduction (35-37). 2. Mindfulness training has shown to alter brain functioning (differently in the short and long run). 3. Mindfulness training uses relevant techniques for improving attentional functioning, both focused attention (top down processing) and open monitoring of present moment experiencing (bottom up processing). 4. ACT has been shown to be effective in improving mental health and physical function in patients with chronic pain, but less so in reducing pain (12, 13). 5. ACT uses mindfulness techniques that do not involve meditation or training, but this may be included in the treatment. The research design thus makes use of a component analysis which is under-utilized in pain treatment research (9, 38). It makes it possible to identify if patients who receive both components (mindfulness training and ACT) obtain more gains than patients who receive only one component. 6. The education program does not involve the same components of change (attentional functioning, learning to live according to ones values and acceptance) as mindfulness and ACT.

4.1.4 The intervention groups

ACT (group 1) will follow a manual based on the work of Steven Hayes and colleagues (10). The manual is adapted to a group therapy setting and includes all the dynamic processes of ACT; committed action, values, self as context, presence in the moment, defusion and acceptance. It has previously been piloted and applied to a work rehabilitation setting by our research group (39). Two qualified therapists will lead every treatment session.

ACT with enhanced mindfulness training (group 2): ACT will be performed exactly as group 1, but in addition mindfulness exercises will be introduced in the ACT sessions and patients will receive audio recordings to aid practice daily at home. The home meditation exercises session will take from 10 to 30 min. and will be based on the program developed by Kabat-Zinn (27).

The education program (group 3) aimed at improving self-management and social identification, will constitute the control group (40). Participants will receive information on relevant topics including pain and symptom management, stress, sleep, eating habits, mental health problems, communication skills and physical activity by a qualified health professional. They will have the opportunity to discuss their thoughts and experiences with the other patients in the group with the aim of strengthening social identity and support, which in turn is expected to foster more healthy management (41). This is regarded as a relevant control group because self-management programs may be cost-effective alternatives to other treatments, with likely effects on psychological well-being, but not on pain and disability (42).

4.1.5 Organization of the groups

The two active treatment programs and the education program all consist of eight four-hour group sessions (eight subjects) during an eight-week period. All therapists will before they are considered qualified receive clinical training within the specific treatment modality during a three month period including two 2-day workshops led by a certified trainer in each field. Each treatment session will be videotaped. A random selection of videotaped sessions will be scored by two experts to establish treatment variance, treatment adherence and treatment competence. Inter-rater reliability will be assessed.

4.1.6 Data collection

Diagnostic status and assessment before inclusion: The four multidisciplinary pain centers have participated in 16 national meetings over the past four years where a common protocol for examining and assessing patients with chronic pain was developed. This is described in a recent study (8) which includes standard examination of neuropathic pain (30) and fibromyalgia (43). Patients will also be examined by a clinical psychologist for concurrent comorbid psychiatric disorder according to Structured Clinical Interview for DSM-5 (44).

Primary outcome measure: Pain intensity measured by the Brief Pain Inventory including four 0-10 numerical rating scales; pain now, least pain, worst pain, average pain (45).

Primary process measures: Attentional functioning will be measured using the attention network test which is specifically designed to measure orienting, alerting and executive attention which can be reported on the patients computer and lasts about 15 min (46).

Secondary outcomes: Physical function and mental health measured by the SF-36 health survey (47), pain catastrophizing (48), fatigue (49), insomnia severity (50), subjective everyday memory problems (51), anxiety and depression (52), pain related beliefs and attitudes about sleep (53) and the five factor mindfulness questionnaire (54).

Measure points: Primary outcome, attentional functioning and secondary outcomes will be assessed before treatment, end of treatment at eight weeks, 16 weeks, 32 weeks, and 52 weeks follow up from the patients' computers after automatic cell-phone call. This is a privacy data security trusted reporting system shown by our research group to be feasible (34). Adherence to mindfulness will be assessed weekly by mobile SMS.

Tertiary outcome measures: Changes in work participation will be analyzed from time of recruitment through one year. The first variable will be dichotomous and defined as participation in competitive work > day (7.5 hours) per week on average over 8 weeks. Days of paid work will be used as total number of days worked (continuous variable) in the follow-up period as a cumulative measure of work productivity. The data will be collected from the register of the Norwegian Labour and Welfare Administration (NAV).

Cost-effectiveness and cost-utility will be assessed from a health service perspective and a societal perspective. The health service perspective will include intervention costs (assessment and treatment) and additional relevant primary and secondary health care costs. A micro-costing approach will be applied for calculation of intervention costs. Data on health service utilization will be collected from national and local registers in addition to a patient reported questionnaire to assure complete and relevant information. The societal perspective will in addition include sick leave/productivity costs based on data from the register of the Norwegian Labour and Welfare. Cost-effectiveness will be assessed by comparing incremental costs to incremental primary and secondary outcomes. For cost-utility, Quality Adjusted Life Years (QALY) will serve as the outcome measure. QALY will be calculated from SF-6D (55) and taking time intervals into account.

Other measures: Age, sex, civil status, education level, work and disability status, smoking, physical activity, diet and lifestyle habits, major life events and frequency (and time) practicing mindfulness.

4.1.5 Statistical power

We calculated sample size based on an assumption of a mean baseline pain intensity of 5.4 with a standard deviation of 2.1 (56) and a 10% reduction in pain intensity in the education group, 20% in the ACT group and 30% in the ACT with mindfulness training group. These improvements may be regarded as minimally important vs moderate changes, respectively (16, 57). For a two-sided test with 5 % significance level and 80% power, we calculated that the number of patients needed to compare ACT with mindfulness to the education group was 58 in each group. Comparing ACT with and ACT without mindfulness training would require 141 in each group, and comparing ACT without mindfulness training to education would require 126 in

each group. We increased group size to 162 participants per group to allow for dropout, to provide equality between groups and for secondary analyses. Both intention to treat and treatment completer analyses will be conducted. A detailed data analysis strategy will be outlined before collecting the data.

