### 3.3 Sample size

The sample size calculations are described in detail in the registered protocol. We calculated sample size based on an assumption of a mean baseline average pain intensity of 5.4 with a standard deviation of 2.1 (Thong et al., 2018) and a 10% reduction in pain intensity in the education group, 20% in the ACT group and 30% in the ACT with mindfulness training

group. These improvements may be regarded as minimally important vs moderate changes, respectively (R. H. Dworkin et al., 2008; Farrar et al., 2001). For a two-sided test with 5 % significance level and 80% power, we calculated that the number of patients needed to compare ACT with mindfulness to the education group was 58 in each group. Comparing ACT with and ACT without mindfulness training would require 141 in each group, and comparing ACT without mindfulness training to education would require 126 in each group. We increased group size to 162 participants per group to allow for dropout, to provide equality between groups and for secondary analyses.

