### 4.3 Analysis populations

The primary analysis will estimate mean difference and 95% confidence interval (CI) in BPI pain intensity score at post-treatment and 52-week follow-up between the two interventions and the active control group (ACT, ACT with enhanced mindfulness and education group). The analyses will be conducted according to the intention-to-treat principle using a linear mixed model for repeated measures. This model includes all available data for all participants at each time point (i.e. baseline, post-treatment, 16 weeks, 32 weeks and 52 weeks). The distribution of the BPI pain intensity score will be assessed, and the variable may be transformed (e.g. log transformation) to better fit with the assumptions for the regression analyses. In the regression model, individual participants will be specified as a random effect, accounting for the within subject covariance structure. The effect of group and time will be specified as fixed effects using a joint variable of intervention and time. Here, baseline levels are pooled over the three study groups assuming that any baseline differences are due to

chance; this also controls for any baseline differences in the outcome variable. The between group difference at 52-week follow-up will be adjusted for the variable used for stratification in the randomisation (i.e., center). Further adjustment for baseline levels of potentially important prognostic factors will also be conducted. We will also use GEE analyses to estimate an odds ratio (with 95% CI) for a two-point change in BPI between the groups taking into account the repeated observations. This analysis will be adjusted for the same factors as those included in the linear mixed model. In addition to the intention to treat analyses, we will conduct per protocol analyses using information on adherence to the trial.

All secondary outcomes will be analysed using a similar approach; for continuous we will use linear mixed models to estimate mean differences between groups, and for ordinal or binary variables we will use logistic GEE analyses to estimate odds ratios. For analyses of mean differences, the distribution of each outcome variable will be assessed to inform possible transformation or initiate alternative analytical procedures. The precision of all estimated effects will be assessed by a 95% CI.

Possible modifiers and mediators of the effect of intervention on the primary and secondary outcomes will be assessed in secondary analyses.

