### **5.2 Recruitment**

The recruitment of participants was conducted in Trondheim, Oslo, Bergen and Tromsø. The recruitment started in March 2020, had to break because of COVID-19, and was completed in April 2023. Further details on recruitment are given in the registered protocol.

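### The 141 and 126 per group for the two 0.54-point comparisons do not follow from the plan's own inputs, which give about 238 for each; 162 per group has about 64% power before baseline adjustment

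*Protocol*

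**What the plan says.** Protocol 4.1.5 (Statistical power) and SAP 3.3 use the same inputs and report the same results. Baseline pain intensity is taken as 5.4 with SD 2.1, and the assumed effects are "a 10% reduction in pain intensity in the education group, 20% in the ACT group and 30% in the ACT with mindfulness training group". The criterion is given as "For a two-sided test with 5 % significance level and 80% power".

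Three group sizes follow:

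- ACT with mindfulness against education: 58 per group.
- ACT with against without mindfulness: "Comparing ACT with and ACT without mindfulness training would require 141 in each group".
- ACT against education: "comparing ACT without mindfulness training to education would require 126 in each group".

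The SAP then states "We increased group size to 162 participants per group to allow for dropout"; equality between groups and secondary analyses are given as further reasons. Neither section gives a formula, a correlation between baseline and follow-up, a dropout rate, or a different SD for any comparison. SAP 3.3 refers to the registered protocol for detail, but the Protocol contains the same figures and no further working.

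The planned analysis (SAP 4.3) is a linear mixed model with baseline pooled over the groups, of which the SAP says "this also controls for any baseline differences in the outcome variable". SAP 3.6 claims a gain in power from repeated measures but does not quantify it.

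**The concern.** The assumed reductions are equally spaced. The step from education to ACT is therefore as large as the step from ACT to ACT with mindfulness, and one SD applies throughout. Two comparisons with the same difference, SD, significance level and power cannot need different numbers, yet the plan gives 126 and 141. Each step is also half of the difference for which 58 is stated, so each should need about four times as many: 4 × 58 = 232. The stated figures are little more than half of that.

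These two comparisons are hypotheses 1 and 2, the subject of the main paper. Both documents present 162 as the requirement with a margin on top. If the requirement is really about 238, then 162 falls short of it on the stated inputs and the margin does not exist. A reader of a null result would wrongly believe that the trial had at least 80% power to detect 0.54 points.

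**Working it through.** **Inputs** (Protocol 4.1.5 Statistical power; SAP 3.3): baseline mean 5.4, SD 2.1, reductions of 10%, 20% and 30%, two-sided 5%, 80% power. The expected means are

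- education: 5.4 × 0.9 = 4.86
- ACT: 5.4 × 0.8 = 4.32
- ACT with mindfulness: 5.4 × 0.7 = 3.78

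The differences d are 1.08 (ACT with mindfulness against education), 0.54 (ACT with against without mindfulness) and 0.54 (ACT against education).

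**Formula.** n per group = 2 × (1.960 + 0.842)² × SD² / d², where (1.960 + 0.842)² ≈ 7.849.

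**The plan's 58.** 2 × 7.849 × 2.1² / 1.08² = 59.4, so 60. With the means rounded to 4.9 and 3.8, d = 1.1 and n = 57.2, so 58. The figure reproduces as an unadjusted two-sample calculation and is not disputed.

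**The plan's 141 and 126.** 2 × 7.849 × 2.1² / 0.54² = 237.4, so 238 per group for each comparison (239 by the t-test). Neither stated figure reproduces.

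**Rounding does not explain them.** Means of 4.9, 4.3 and 3.8 give d = 0.6 for ACT against education (n = 193) and d = 0.5 for ACT with against without mindfulness (n = 277).

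**No common adjustment explains them.** Under any common SD, correlation, significance level and power, d is proportional to 1/√n, and the two smaller differences must add up to the larger one.

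- 1/√141 + 1/√126 = 0.0842 + 0.0891 = 0.1733
- 1/√58 = 0.1313
- The n implied for the third comparison is 1/0.1733² ≈ 33, not 58.

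In points at SD 2.1, 141 corresponds to 0.70 and 126 to 0.74 (sum 1.44), while 58 corresponds to 1.09. One-sided testing, SD proportional to the mean, a log scale, paired, change-score and covariance-adjusted versions, and a three-group analysis of variance were also tried. None gives all three figures.

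**Power for d = 0.54** (two-sample t-test). For baseline adjustment the SD is multiplied by √(1 − r²), where r is an assumed correlation between baseline and week 52.

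| Analysed per group | Unadjusted | r = 0.5 | r = 0.6 | r = 0.7 |
|---|---|---|---|---|
| 126 | 53% | – | – | – |
| 141 | 58% | – | – | – |
| 162 | 64% | 76% | 82% | 90% |
| 130 | 54% | 66% | 73% | 82% |

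The row for 130 is an illustration: 162 × 0.8 ≈ 130. The plan states no trial dropout rate. The 20% loss borrows from the clinics' routine records, for which Protocol section 2 gives a response of "almost 100% pre-admission and about 80% one year after treatment".

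**Correlation needed for 80% power.** At 162, r = √(1 − 162/237.4) = 0.56. At 130, r = √(1 − 130/237.4) = 0.67.

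**Difference detectable with 80% power, unadjusted.** About 0.66 points at 162 and 0.73 at 130.

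**The larger comparison.** For d = 1.08, power at 162 is over 99%.

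**The case against.** The strongest reply is that 238 belongs to an unadjusted comparison at one time point, which is not the planned analysis. The mixed model uses baseline and all follow-up visits, and with a plausible correlation 162 per group could reach 80% with some margin. This stands, and for that reason the finding does not say that the planned model is underpowered. It does not rescue 141 and 126. A common adjustment would shrink all three figures in proportion, yet 58 is the unadjusted figure.

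The SD of 2.1 is stated for baseline, and no follow-up SD is given. If the 52-week SD were smaller, less would be needed: an assumed SD of 1.7 gives 2 × 7.849 × 1.7² / 0.54² ≈ 156 per group. The 64% is therefore conditional on the stated SD. A different common SD still cannot produce unequal figures for two equal differences.

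The illustration with 130 counts completers only. The mixed model also uses data from patients who miss week 52, so those powers are slightly too low for it.

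Finally, recruitment is over and results will be reported as estimates with 95% confidence intervals, so the correction changes no result. It does change what both documents tell the reader about the trial's ability to detect the effects it was designed for. Overwriting historical figures without comment would be wrong, which bears on how the correction is made.

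**Conclusion.** The concern holds. On the stated inputs each 0.54-point comparison needs about 238 per group, not 141 or 126, and the three published figures contradict one another. Unadjusted power at 162 per group is about 64%, so for these two comparisons the claimed allowance above the requirement is not there on the plan's own numbers.

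This reads the percentage reductions as fractions of the common baseline mean and takes 2.1 as the SD in every group at 52 weeks; under that reading 58 reproduces. Power under the planned mixed model is undetermined, because it depends on a correlation, a retention rate and a follow-up SD that the plan does not give. The comparison of ACT with mindfulness against education is unaffected. How 141 and 126 arose cannot be told from the documents.

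**What to change.** Make a dated correction in SAP 3.3, with a matching note to Protocol 4.1.5 (Statistical power), that leaves the reported figures visible:

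- State that 141 and 126 do not follow from the inputs, and give 238 per group for each 0.54-point comparison in their place. The 58 may stand.
- State that 162 per group gives about 64% power for these two comparisons without baseline adjustment, or give the power of the planned model under an explicit and justified correlation, follow-up SD and dropout rate.
- Give the detectable difference: about 0.66 points at 162, unadjusted.
- Remove the implication that 162 secures 80% power plus a dropout margin for hypotheses 1 and 2.

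No further enrolment is asked for: SAP 5.2 says that recruitment "had to break because of COVID-19, and was completed in April 2023". The cost is wording in two documents and a less favourable stated power. Estimand, model and data are unchanged.
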